### **3.3.1 Pharmaceutical and Therapeutic Background**

#### **3.3.1.1 Pembrolizumab**

The importance of intact immune surveillance function in controlling outgrowth of neoplastic transformations has been known for decades [Disis, M. L. 2010]. Accumulating evidence shows a correlation between tumor-infiltrating lymphocytes in cancer tissue and favorable prognosis in various malignancies. In particular, the presence of CD8+ T cells and the ratio of CD8+ effector T cells/FoxP3+ regulatory T cells (Tregs) correlates with improved prognosis and long-term survival in solid malignancies. These include ovarian, colorectal, pancreatic; hepatocellular; melanoma, and renal cell carcinomas. Tumor-infiltrating lymphocytes can be expanded ex vivo and reinfused, inducing durable objective tumor responses in cancers such as melanoma [Dudley, M. E., et al 2005] [Hunder, N. N., et al 2008].

The PD-1 receptor-ligand interaction is a major pathway hijacked by tumors to suppress immune control. The normal function of PD-1, expressed on the cell surface of activated T cells under healthy conditions, is to down-modulate unwanted or excessive immune responses, including autoimmune reactions. PD-1 (encoded by the gene *Pdcd1*) is an immunoglobulin (Ig) superfamily member related to cluster of differentiation 28 (CD28) and CTLA-4 that has been shown to negatively regulate antigen receptor signaling upon engagement of its ligands (PD-L1 and/or PD-L2) [Greenwald, R. J., et al 2005] [Okazaki, T., et al 2001].

The structure of murine PD-1 has been resolved [Zhang, X., et al 2004]. PD-1 and its family members are type I transmembrane glycoproteins containing an Ig-variable-type (IgV-type) domain responsible for ligand binding and a cytoplasmic tail responsible for the binding of signaling molecules. The cytoplasmic tail of PD-1 contains 2 tyrosine-based signaling motifs, an immunoreceptor tyrosine-based inhibition motif, and an immunoreceptor tyrosine-based switch motif. Following T cell stimulation, PD-1 recruits the tyrosine phosphatases, SHP-1 and SHP-2, to the immunoreceptor tyrosine-based switch motif within its cytoplasmic tail, leading to the dephosphorylation of effector molecules such as CD3 zeta (CD3ζ), protein kinase C-θ (PKCθ), and zeta-chain-associated protein kinase (ZAP70), which are involved in the CD3 T cell signaling cascade [Okazaki, T., et al 2001] [Chemnitz, J. M., et al 2004] [Sheppard, K-A, et al 2004] [Riley, J. L. 2009]. The mechanism by which PD-1 down-modulates T cell responses is similar to, but distinct from, that of CTLA-4, because both molecules regulate an overlapping set of signaling proteins [Parry, R. V., et al 2005] [Francisco, L. M., et al 2010]. As a consequence, the PD-1/PD-L1 pathway is an attractive target for therapeutic intervention in advanced NSCLC.

#### **3.3.1.2 MK-1308 (Anti-CTLA-4)**

MK-1308 is a humanized, antagonist IgG1 mAb that binds CTLA-4 and blocks its interaction with both of its ligands, CD80 (B7.1) and CD86 (B7.2).

CTLA-4 is a negative regulator of T-cell function and proliferation. It is found on the surface of activated T cells and Tregs as a single-pass transmembrane protein belonging to the immunoglobulin superfamily. CTLA-4 was identified as a second receptor for both CD80 and CD86 and shares some structural homology with the activating co-receptor, CD28.

Unlike CD28, which is expressed on naïve T cells, the cell surface expression of CTLA-4 is both transient and tightly regulated. The opposing responses mediated by these 2 receptors are capable of coordinating the strength of the immune system's response.

As part of the adaptive immune response, T cells are central to mounting a defense against tumor growth. Activation of T cells is achieved via the dual engagement of both the T-cell receptor and CD28 receptor on the T cell to mount a full immunogenic response. CD28 binds to either CD80 or CD86 molecules expressed on antigen-presenting cells, leading to T-cell specific expression and presentation of CTLA-4, which then competes with CD28 to bind these activating molecules with a high affinity, thereby dampening the activation signal for the T cell, moving it to a more tolerogenic state. Therefore, blocking this immune checkpoint, allowing T cells to remain active, would allow the immune system to mount a more competent and durable antitumor response.

CTLA-4 suppression is thought to be primarily at sites of T-cell activation, eg, secondary lymph organs rather than within the tumor microenvironment; however, inhibition of CTLA-4 results in substantial increases of T cell infiltrates within tumor tissues. This contrasts with the presumed inhibition of T-cell function via PD-1 engagement, which occurs within the tumor microenvironment between T cells interacting with both antigen-presenting cells and the tumor cells themselves. Differences in mechanism and expression of these receptors and their ligands suggest that these differential mechanisms of action may underlie the observed clinical benefit when used as combination therapy above their respective monotherapies.

The humanized anti-human CTLA-4 antibody is being proposed for development in combination with the Sponsor's anti-PD-1 mAb, pembrolizumab. Two human mAbs targeting CTLA-4, ipilimumab (IgG1) and tremelimumab (IgG2), have been and continue to be evaluated in the clinic for the treatment of various oncology indications. Ipilimumab was approved for melanoma patients alone and in combination with the anti-PD-1 antibody. Ipilimumab demonstrates efficacy with doses from 1 to 10 mg/kg, with lower toxicity rates at lower doses. In Checkmate 227, the Phase 3 study of the combination in NSCLC, ipilimumab is being administered at a 1 mg/kg dose every 6 weeks (Q6W) [ClinicalTrials.gov 2017]. The combination of ipilimumab and nivolumab is being actively pursued in clinical studies in multiple cancer types.

### **3.3.1.3 MK-4280 (Anti-LAG-3)**

MK-4280 is a potent and highly selective antagonistic humanized mAb of the IgG4/kappa isotype with a hinge stabilized (ser228Pro) modification designed to directly block the interaction between LAG-3 and its ligand, MHC Class II.

Lymphocyte-activation gene 3 (LAG-3) is an inhibitory immune modulatory receptor that regulates effector T cell homeostasis, proliferation, and activation, and has a role in the suppressor activity of regulatory T cells ( $T_{\text{regs}}$ ) [Huang, C. T., et al 2004] [Baixeras, E., et al 1990] [Goldberg, M. V. and Drake, C. G. 2011]. Lymphocyte-activation gene 3 is expressed on activated  $CD8^{+}$  and  $CD4^{+}$  T cells,  $T_{\text{regs}}$  and the  $T_{\text{r1}}$  regulatory T cell population, as well as on natural killer cells and a subset of tolerogenic plasmacytoid dendritic cells. Because of its proposed role on both effector T cells and  $T_{\text{regs}}$ , LAG-3 is one of several immune checkpoint

molecules where simultaneous blockade of both cell populations has the potential to enhance antitumor immunity [Andrews, L. P., et al 2017].

LAG-3 is structurally related to cluster of differentiation 4 (CD4) and a member of the immunoglobulin (Ig) superfamily. Like CD4, its ligand is MHC Class II molecules [Huard, B., et al 1995] [Triebel, F., et al 1990]. Interaction with its ligand leads to dimerization and signal transduction resulting in altered T cell activation. Following T cell activation, LAG-3 is transiently expressed on the cell surface. A large proportion of LAG-3 molecules are found in intracellular stores and can be rapidly translocated to the cell membrane upon T cell activation [Woo, S. R., et al 2010]. LAG-3 expression is regulated at the cell surface by extracellular cleavage to yield a soluble form of LAG-3 (sLAG-3), which can be detected in serum [Li, N., et al 2007]. Expression of LAG-3 is tightly regulated and represents a self-limiting mechanism to counter uncontrolled T cell activity.

LAG-3 is commonly co-expressed with PD-1 on anergic/exhausted T cells, and both in vitro and in vivo data indicate that dual blockade of LAG-3 and PD-1 can have a synergistic impact on reversing tumor-specific anergy [Pardoll, D. M. 2012] [Blackburn, S. D., et al 2009] [Grosso, J. F., et al 2009]. Indeed, LAG-3 was selected as an initial target of interest based on published data indicating that the addition of an anti-LAG-3 antibody could enhance the activity of an anti-PD-1 antibody in rodent, preclinical tumor models. In addition to the data from preclinical models using anti-mouse antibodies, data from double knock-out mice (LAG-3-/-PD-1-/-) show the ability to resist growth of various tumor implants, indicating a clear synergy between these molecules [Woo, S. R., et al 2012]. These data support the rationale of the combination MK-4280 (anti-LAG-3) with pembrolizumab in this study.

#### **3.3.1.4 Lenvatinib**

Angiogenesis, the formation of new blood vessels from a pre-existing vascular network, is essential for tumor growth and metastasis. VEGF and its family of receptors (VEGRs 1-3) play a major role in tumor angiogenesis [Ferrara, N., et al 2003] [Ellis, L. M. and Hicklin, D. J. 2008] [Tammela, T. and Alitalo, K. 2010]. Accumulated evidence suggests that FGF and its receptor tyrosine kinase, FGFR also play important roles for tumor angiogenesis [Cross, M. J. and Claesson-Welsh L. 2001] [Lieu, C., et al 2011] [Limaverde-Sousa, G., et al 2014].

Lenvatinib is a potent multiple RTK inhibitor that selectively inhibits VEGF receptors, VEGFR1 (FLT1), VEGFR2 (KDR), and VEGFR3 (FLT4), FGFR1-4, PDGFR $\alpha$ , KIT, and RET. Among known kinase inhibitors in clinical use, lenvatinib is one of the only inhibitors currently labeled with a mechanism of action as an inhibitor of not only VEGFRs but also FGFRs, both of which are currently believed to be very important for tumor angiogenesis.

Lenvatinib inhibited cell free kinase activities for VEGFR1-3 and FGFR1-3 with Ki values around 1 nmol/L, and 8-22 nmol/L, respectively. In cell-based assays, lenvatinib inhibited VEGF-derived and FGF-derived tube formation of HUVEC with IC50 values of 2.1 and 7.3 nmol/L, respectively. Analysis of the signal transduction molecules revealed that lenvatinib inhibited both the MAPK pathway and the mTOR-S6K-S6 pathway in HUVECs triggered by activated VEGFR and FGFR. Furthermore, lenvatinib (10, 30 mg/kg) significantly inhibited both VEGF- and FGF-driven angiogenesis in a murine in vivo model [Yamamoto, Y., et al 2014]. In vivo, lenvatinib exhibited antitumor activity against various

human tumor xenografts in athymic mice including 5 types of thyroid carcinomas (differentiated [papillary and follicular], anaplastic, squamous, and medullary thyroid carcinomas), RCC, HCC, melanoma, gastric cancer, NSCLC, ovarian cancer, Ewing's sarcoma, and osteosarcoma. In addition, the antitumor activity of lenvatinib in combination with other anticancer agents in several xenograft models was greater than that of lenvatinib or the other agents alone.

In summary, lenvatinib inhibited VEGF-driven VEGFR2 phosphorylation and suppressed proliferation and tube formation in human umbilical vein endothelial cell (HUVEC) models. Antitumor activity of lenvatinib in vivo has been shown in numerous xenograft animals. These results suggest that lenvatinib may be a novel anticancer therapy through inhibition of angiogenesis and may be useful as either monotherapy or in combination with other anticancer drugs.

### **3.3.2 Preclinical and Clinical Studies**

#### **3.3.2.1 Pembrolizumab (MK-3475)**

Information regarding preclinical studies with pembrolizumab may be found in the current edition of the IB.

#### **3.3.2.2 MK-1308**

The monovalent affinities of MK-1308 against human CTLA-4 are approximately 2- to 3-fold tighter [REDACTED] MK-1308 showed comparable binding to human and [REDACTED]

The ability of the antibodies to block binding of human CTLA-4 to its natural ligands, CD80 and CD86, was assessed by cell-based enzyme-linked immunosorbent assay (ELISA) using [REDACTED]

[REDACTED] MK-1308 also induce the upregulation of IL-2 in a dose-dependent manner with a comparable potency to either clinical standard. Consistent with this finding, [REDACTED] induced dose-dependent IFN-gamma production from CD4+ T cells in a mixed lymphocyte reaction (MLR)-based assay, using activated CD4+ T cells and allogenic differentiated monocytes to serve as DCs. MK-1308 induced the upregulation of IFN-gamma in a dose-dependent manner with observed efficacy [REDACTED] The inclusion of pembrolizumab in combination with either MK-1308 [REDACTED] resulted in a substantial and synergistic increase in IFN-gamma production in the current MLR format.

More detailed information of preclinical studies with MK-1308 may be found in the current edition of the IB.

### **3.3.2.3 MK-4280**

Efficacy studies in mouse models have shown that administration of antibodies blocking LAG-3/MHC Class II interaction in combination with anti-PD-1 antibodies enhances immune responses and leads ultimately to tumor rejection. Anti-mouse LAG-3 antibodies have demonstrated antitumor responses as combination therapy with anti-PD-1 in syngeneic tumor models of multiple cell-type origins (eg, fibrosarcoma, renal cell carcinoma, bladder carcinoma, and colorectal carcinoma). Preclinical models have shown both overall tumor growth inhibition and an increase in the number of tumor-free mouse treatment groups (Bristol Myers Squibb Company LAG-3 Antibody Patent; International Publication Number: WO 2015/042246 A1).

### **3.3.2.4 Lenvatinib**

In preclinical models, lenvatinib showed a superior antitumor activity in immune-competent mice compared to in immune-deficient mice suggesting that lenvatinib may have immune modulating effects. Indeed, lenvatinib decreased the tumor associated macrophage (TAM) population while increasing the percentage of IFN-gamma producing CD8+ T cells in regional lymph nodes [Kato, Y., et al 2015]. The antitumor activity of lenvatinib, single-agent anti-mouse PD-1 mAb and the combination treatment of lenvatinib and anti-mouse PD-1 mAb was examined in syngeneic mouse models [Kato, Y., et al 2015]. Combination of lenvatinib with PD-1 mAb showed more potent inhibitory activity against tumor growth in 3 syngeneic mouse models (LL/2 murine lung carcinoma, H22 murine hepatocellular carcinoma, and CT26 murine colon cancer) compared with each single agent alone [Kato, Y., et al 2016]. While single agent PD-1 mAb treatment resulted in an increase in both Th1 and Th2 cytokines, lenvatinib monotherapy alone decreased Th2 cytokines, and combination treatment increased Th1 cytokines but decreased Th2 cytokines [Kato, Y., et al 2016].

As noted in the prescribing information for LENVIMA® (lenvatinib) capsules, for oral use, lenvatinib is currently used to treat “patients with locally recurrent or metastatic, progressive, radioactive iodine-refractory DTC” [differentiated thyroid cancer] and is used “in combination with everolimus” to treat “patients with advanced RCC [renal cell carcinoma] following one prior anti-angiogenic therapy.”

## **3.3.3 Ongoing Clinical Studies**

### **3.3.3.1 Pembrolizumab (MK-3475)**

Over 300 interventional clinical studies involving pembrolizumab are currently ongoing in a number of advanced solid tumor indications, as well as in hematological malignancies. For further details, please refer to the current edition of the IB.

### **3.3.3.2 MK-1308**

The first human clinical study with MK-1308 is currently ongoing (MK-1308-001). This Phase 1 study evaluates MK-1308 as monotherapy for 1 cycle and in combination with pembrolizumab in study participants with advanced solid tumors. The study is a multi-site, open-label study of MK-1308 monotherapy and MK-1308 in combination with pembrolizumab (Part 1, dose escalation) followed by dose confirmation therapy of MK-1308

and pembrolizumab (Part 2, Arms A, B, C). Dose confirmation for Arms A, B, and C include first-line, treatment-naïve, advanced/metastatic NSCLC. Study participants will be treated with 200 mg pembrolizumab Q3W plus MK-1308 25 mg Q3W (Arm A), 25 mg Q6W (Arm B), and 75 mg Q6W (Arm C). From a preliminary analysis of MK-1308-001 safety, anti-tumor activity, PK and pharmacodynamic biomarker data collected during the Dose Escalation and Dose Confirmation phases of the study the RP2D for MK-1308 to carry forward was determined to be 25 mg given every 6 weeks. The ORR of MK-1308 25 mg administered every 6 weeks in the advanced 1L NSCLC population (Arm B) was similar to that of the 75 mg dose level given every 6 weeks (36% versus 28%) at this data cutoff date. The safety at this dose and schedule however was superior, with a 14% Grade 3-5 related adverse event rate (Arm B) versus a 28% Grade 3-5 adverse event rate (Arm C).

### **3.3.3.3 MK-4280**

The first clinical study with MK-4280 is currently ongoing. The safety and tolerability of MK-4280 as monotherapy and in combination with pembrolizumab are evaluated in study participants with advanced solid tumors. This is a Phase 1, multi-site, open-label study of MK-4280 monotherapy (Part A, Arm 1) and MK-4280 in combination with pembrolizumab (Part A, Arm 2) followed by dose confirmation of the combination (Part B) with expansion cohorts to assess antitumor efficacy.

Preliminary PK data from participants treated during Part A of MK-4280-001 (MK-4280 alone and in combination with pembrolizumab) at doses from 7 mg to 700 mg showed that serum MK-4280 exposures increased in a dose-dependent manner and preliminary PK analysis of MK-4280 exposures suggest that target receptor-mediated clearance of MK-4280 was saturated at the 210 mg and 700 mg doses. Also, preliminary data for the exploratory target engagement pharmacodynamic marker from participants treated during Part A of MK-4280-001 also showed a dose-dependent increase in total soluble LAG-3 in serum, generally approaching saturation at the 210 mg and 700 mg doses. MK-4280-001 has also shown the combination of MK-4280 and pembrolizumab to be well tolerated, with no DLTs observed in any participants (N=277) treated with escalating doses of MK-4280 (ranging from 7 mg to 800 mg) as monotherapy and in combination with pembrolizumab as of the data cutoff of 04-JAN-2019. Thirty-nine participants with gastric cancer have been treated with MK-4280 700 mg Q3W as noted in the MK-4280 IB.

Based on a preliminary analysis of DLTs and safety data, along with preliminary PK and exploratory pharmacodynamic observations, a preliminary RP2D of 200 mg Q3W was determined for MK-4280. Later, based on accumulating data from the study, the Sponsor elected to revise the preliminary RP2D for MK-4280 to 800 mg Q3W. As of 09-AUG-2019, 61 participants have been treated with the 800 mg MK-4280 dose in the MK-4280-001 study, including 20 on monotherapy and 41 on combination therapy with pembrolizumab. Twenty participants have passed the DLT period; 10 participants on monotherapy and 10 participants on combination therapy, and there have been 0 DLTs. Therefore, the proposed dose of MK-4280 is changed to 800 mg Q3W in this protocol amendment.

### **3.3.3.4 Lenvatinib**

Lenvatinib was chosen for this study based on the results of the Phase 1b portion of KN146/HOPE111, the primary endpoint of which was to determine the MTD and RP2D for

lenvatinib when used in combination with pembrolizumab 200 mg IV, Q3W. Thirteen participants (lenvatinib 24 mg/day + pembrolizumab 200 mg IV Q3W: n=3; lenvatinib 20 mg/day + pembrolizumab 200 mg: n=10) were enrolled in the Phase 1b portion of the study. Eight of the participants had RCC, 2 had NSCLC, 2 had EC, and 1 had melanoma. There were 2 dose-limiting toxicities (DLTs) at the lenvatinib 24 mg/day + pembrolizumab 200 mg dose IV Q3W (1 participant had Grade 3 arthralgia, and another had Grade 3 fatigue); hence, this was defined as the toxic dose. No DLTs were reported in the next 10 participants (expansion part), all of whom received the lenvatinib 20 mg/day plus pembrolizumab 200 mg IV Q3W dose. Based on review of all of the clinical data from these 13 participants, the MTD and RP2D were determined to be 20 mg lenvatinib daily in combination with a fixed dose of 200 mg pembrolizumab given IV Q3W. In Phase 1b, 2 of 13 participants had NSCLC (1 PR and 1 stable disease) [Taylor, M., et al 2016]. Lenvatinib demonstrated meaningful antitumor activity and an acceptable safety profile in a Phase 2 study in patients with RET fusion-positive lung adenocarcinoma. A response rate of 16% and median PFS of 7.3 months with median OS not reached was observed after up to 24 months of follow-up. Overall survival at 24 months was 54.5%, not yet reached in the Other RET fusion group and 11.4 months in the KIF5B-RET fusion group. Lenvatinib has also been studied in unselected patients with non-squamous NSCLC (i.e., not screened for the presence of RET-fusions) who have failed at least two prior systemic anticancer regimens. In this study, the observed ORR was 10.1%, and the median PFS was 5.2 months [Havel, L., et al 2014]. Additionally, there is a Phase 3 clinical study ongoing for lenvatinib combined with pembrolizumab in renal cell carcinoma. These clinical data suggest a value in pembrolizumab combined with lenvatinib, and therefore this agent was selected for further study.

### **3.4 Benefit/Risk Assessment**

It cannot be guaranteed that participants in clinical studies will directly benefit from treatment during participation, as clinical studies are designed to provide information about the safety and effectiveness of an investigational medicine.

Additional details regarding specific benefits and risks for participants participating in this clinical study may be found in the accompanying IBs and Informed Consent documents.

#### 4 Objectives/Hypotheses and Endpoints

This study will evaluate study participants with advanced non-small cell lung cancer (NSCLC) without prior systemic treatment for their advanced disease:

Objective/Hypothesis	Endpoint
Primary	

Objective: To evaluate the clinical activity (as assessed by objective response rate [ORR]) of specific pembrolizumab-based combinations.

Primary Hypotheses:

The ORR will be greater than CCI among participants with low GEP and low TMB receiving pembrolizumab in combination with MK-1308, MK-4280, or lenvatinib.

The ORR will be greater than CCI among participants with low GEP and high TMB receiving pembrolizumab in combination with MK-1308, MK-4280, or lenvatinib.

The ORR will be greater than CCI among participants with high GEP and low TMB receiving pembrolizumab in combination with MK-1308, MK-4280, or lenvatinib.

The ORR will be greater than CCI among participants with high GEP and high TMB receiving pembrolizumab in combination with MK-1308, MK-4280, or lenvatinib.

	

ORR: Participants who have a confirmed complete response (CR) or partial response (PR) per Response Evaluation Criteria in Solid Tumors 1.1 (RECIST 1.1) as assessed by local site.

Objective/Hypothesis	Endpoint
Secondary	

 
Objective: To evaluate the clinical activity (as assessed by progression-free survival [PFS] and overall survival [OS]) of specific pembrolizumab-based combinations. PFS and OS to different specific pembrolizumab-based combinations will be assessed independently in each biomarker-defined group.
 
	
 
PFS Time from randomization to the first documented disease progression per RECIST 1.1 as assessed by local site or death, whichever occurs first.
 
OS: Time from randomization to death due to any cause.
 


 
Objective: To determine the safety and tolerability of pembrolizumab in combination with MK-1308, MK-4280, or lenvatinib. Safety and tolerability to different specific pembrolizumab-based combinations will be assessed independently in each biomarker-defined group.
 
	
 
Number of Participants Experiencing Adverse Events (AEs).
 
Number of Participants Discontinuing Study Drug Due to AEs.
 

Tertiary/Exploratory	

Biomarkers for different specific pembrolizumab-based combinations will be assessed independently in each biomarker-defined group.
 
 
Objective: To evaluate the clinical activity (as assessed by ORR and PFS) using modified RECIST 1.1 for immune-based therapeutics (iRECIST) [Seymour, L., et al 2017], as assessed by local site review.
 
Objective: To evaluate clinical responses based upon individual biomarkers (PD-L1 immunohistochemistry [IHC] GEP and TMB).
 
Objective: To explore additional classifiers of primary resistance to PD-1 blockade beyond GEP and TMB based on additional immune evaluation of baseline tissue.
 
Objective: To assess the concordance in neoantigen mutation load as measured by TMB gene panel vs whole exome sequencing/RNA-seq
 
	
 
Clinical activity (as assessed by ORR and PFS) of specific pembrolizumab-based combinations using modified RECIST 1.1 for immune-based therapeutics (iRECIST), as assessed by local site review.
 

Objective/Hypothesis	Endpoint

 
Objective: To identify molecular (genomic, metabolic, and/or proteomic) biomarkers that may be indicative of clinical response/resistance, safety, pharmacodynamic activity, and/or the mechanism of action of pembrolizumab based combinations.
 
Objective: To collect and build on the pharmacokinetic (PK) and anti-drug antibody (ADA) experiences of MK-1308 and MK-4280 in combination with pembrolizumab.
 
	
 
Germline genetic variation, genetic (DNA) mutations from tumor, tumor and blood RNA variation, proteomics and IHC, and other blood-derived biomarkers.
 
PK profiles and ADA rates of MK-1308 and MK-4280 in combination with pembrolizumab
 

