Therefore, based on the totality of preliminary data accumulated so far, the Sponsor has elected to change the recommended Phase 2 dose of MK-4280. In order to minimize dosing complexity and lessen the risk of dosing errors given the 200 mg vial size, an 800 mg Q3W dose of MK-4280 alone or in combination with pembrolizumab has been selected as the RP2D and the combination of MK-4280 and pembrolizumab will be tested in the KEYNOTE-495 study.

As of 09-AUG-2019, 61 participants have been treated with 800 mg of MK-4280 in MK-4280-001, including 20 on monotherapy and 41 on combination therapy with pembrolizumab. Twenty participants have passed the DLT period; 10 participants on monotherapy and 10 participants on combination therapy and there have been 0 DLTs.

Participants enrolled under Amendment 05 or later will be treated with pembrolizumab plus MK-4280 800 mg Q3W. Participants enrolled prior to Amendment 05 were initially treated with pembrolizumab plus MK-4280 200 mg Q3W. Upon approval of Amendment 05, participants currently treated with MK-4280 200 mg can choose to stay at this dose level or start MK-4280 800 mg Q3W.

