#### **7.3.1 Adaptive Randomization**

Study participants will first be assigned to a biomarker-defined group ( $\text{GEP}^{\text{low}}\text{TMB}^{\text{low}}$ ,  $\text{GEP}^{\text{low}}\text{TMB}^{\text{hi}}$ ,  $\text{GEP}^{\text{hi}}\text{TMB}^{\text{low}}$ , or  $\text{GEP}^{\text{hi}}\text{TMB}^{\text{hi}}$ ) based on screening test results of TMB and GEP assays.

Due to the different start time of three combination treatments, unequal randomization ratio may be used first, and then randomization schedules will be adjusted to equalize treatment arm enrollment per biomarker-defined group depending on the time of introducing the delayed combination treatments in order to meet study analysis milestones.

For each biomarker-defined group, the first interim analysis will occur after at least 10 participants in each treatment combination have at least 12 weeks of follow-up. After the first interim analysis, participants' response data will be closely monitored throughout the study, and the subsequent interim analyses may be performed with a minimum of 2 additional participants achieving 12 weeks of follow-up for each combination therapy that still remains in the study. At each interim analysis, there will be an opportunity to drop individual treatment combinations within biomarker-defined groups or entire biomarker-defined groups for futility or safety. As long as any biomarker-defined group and treatment combination are retained in the study, enrollment will continue with equal randomization to the remaining treatment arms (see details in Section 10.7).

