## 10 Statistical Analysis Plan

### 10.1 Statistical Analysis Plan Summary

This section outlines the statistical analysis strategy and procedures for the study. Changes in analyses made after the protocol has been finalized, but prior to final database lock, will be documented in a supplemental statistical analysis plan (sSAP) and referenced in the clinical study report (CSR) for the study. Post-hoc exploratory analyses will be clearly identified in the CSR. The study will use an adaptive approach, with on-treatment data guiding study adaptation and success or futility of each combination in each study subpopulation.

Currently, 30 participants are being treated with MK-4280 200 mg Q3W, including 10, 7, 8, and 5 participants in Biomarker Group I, II, III, and IV, respectively. These 30 participants treated with MK-4280 200 mg Q3W may be replaced with 30 additional participants treated with MK-4280 at 800 mg Q3W after the approval of Amendment 05. Consequently, the total treated sample size is changed from 288 to 318. The replacement number may depend on results of interim analyses, including estimated posterior probabilities of meeting the target response rate at the 800 mg dose. All key statistical elements in this section including, but not limited to, statistical efficacy, futility, sample size and power are based on participants receiving pembrolizumab at a dose of 200 mg Q3W in combination with 25 mg MK-1308 Q6W, 800 mg Q3W MK-4280 and lenvatinib daily. The combination with MK-4280 in this section is specifically referring to the participants treated with the combination pembrolizumab with 800 mg MK-4280 Q3W from C1D1 unless more details are provided.

Key elements of the SAP are summarized below; comprehensive details are provided in Sections 10.2 through 10.12.

Study Design Overview	This is an unblinded, open-label adaptively randomized Phase 2 study of a biomarker-directed, pembrolizumab-based (MK-3475-based) combination therapy in study participants with advanced NSCLC.

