## **10.5.2 Safety Analysis Population**

The ASaT population will also be used for the analysis of safety data in this study. At least 1 laboratory or vital sign measurement obtained subsequent to at least 1 dose of study treatment is required for inclusion in the analysis of each specific parameter. To assess change from baseline, a baseline measurement is also required.

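### Safety is planned by biomarker group with no stated summary per combination across groups, and the plan does not settle how the 30 MK-4280 200 mg starters enter the safety tables

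*Combined protocol and SAP*

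**What the plan says.** **Unit of assessment.** The Synopsis (Section 1) and Section 4 set a secondary objective on the safety and tolerability of pembrolizumab with each of the three partners. The next sentence reads "Safety and tolerability to different specific pembrolizumab-based combinations will be assessed independently in each biomarker-defined group". Section 10.6.2 calls for clinical review and a descriptive tabulation of adverse events. It does not say whether events are tabulated by biomarker group, by combination over all groups, or by MK-4280 dose.

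**Who counts as MK-4280.** Section 10.1 states that "All key statistical elements in this section including, but not limited to, statistical efficacy, futility, sample size and power are based on participants receiving pembrolizumab" on the listed regimens, with MK-4280 at 800 mg. It then defines the MK-4280 combination for the whole of Section 10 as participants treated "with 800 mg MK-4280 Q3W from C1D1 unless more details are provided".

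**Safety population.** Section 10.5.2 states: "The ASaT population will also be used for the analysis of safety data in this study". Section 10.5.1 defines ASaT as all allocated participants who received treatment, with no condition on dose.

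**The 200 mg starters.** Sections 5.2 and 10.1 report 30 participants on MK-4280 200 mg: 10, 7, 8 and 5 in Groups I to IV. Under Section 5.5.2.2, "participants currently treated with MK-4280 200 mg can choose to stay at this dose level or start MK-4280 800 mg Q3W".

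**The concern.** Two things are at stake.

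The first is precision. The safety question is about a combination, but the only unit of assessment that the plan names is a combination within a biomarker group. Section 3.2 justifies the groups by response and resistance. An exploratory objective in Section 4 mentions molecular markers of safety, but nothing explains why GEP or TMB status should change toxicity enough to make the group the main unit. Reported only cell by cell, an uncommon adverse event would be described far less precisely than the trial's own data allow.

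The second is the content of the MK-4280 safety tables. Either reading of Section 10 gives a worse table than necessary. If the 800 mg definition governs safety, 30 exposed participants are missing. If ASaT governs, and the starters join one MK-4280 column, events on 200 mg and events after a switch to 800 mg are mixed with those of participants on 800 mg throughout. No rule says which dose an event belongs to.

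**Working it through.** **Step 1: reproduce the plan's totals.** Section 10.7 gives maxima of about 66 in each of Groups I to III and about 90 in Group IV, not counting the 200 mg starters.
- 3 × 66 + 90 = 288
- 10 + 7 + 8 + 5 = 30
- 288 + 30 = 318

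Both stated totals, 288 and 318, are reproduced.

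**Step 2: cell sizes.** There are 3 combinations × 4 groups = 12 cells. An equal split at full enrolment gives 66/3 = 22 and 90/3 = 30. These are averages. Section 10.7 caps a cell at about 25 (Groups I to III) or 40 (Group IV), and the first interim look comes when each combination has at least 10 participants with 12 weeks of follow-up. A cell can therefore end anywhere from about 10 to about 25 or 40.

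**Step 3: pooled size.** With an equal split and no arm dropped, each combination has 3 × 22 + 30 = 96.

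**Step 4: precision.** The zero-event bound is the one-sided 95% limit, 1 − 0.05^(1/n). The chance of at least one case is 1 − (1 − p)^n. The intervals are two-sided 95% Clopper-Pearson, at the whole count nearest to 20%. The 2% and 20% rates are illustrative, because the plan gives no planning rate for adverse events.

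| n | Zero-event upper bound | Chance of ≥1 case at a 2% rate | Interval near 20% |
|---|---|---|---|
| 22 (average cell, Groups I-III) | 12.7% | 36% | 4/22: 5.2-40.3% |
| 30 (average cell, Group IV) | 9.5% | 45% | 6/30: 7.7-38.6% |
| 96 (pooled combination) | 3.1% | 86% | 19/96: 12.4-29.2% |

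The direction does not depend on full enrolment. A cell that stops at 10 has a zero-event bound of 25.9%. Four such cells pooled (n = 40) give 7.2%, which is also the bound for the largest single cell, Group IV at its cap.

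**Step 5: the 30 starters.** With all 30 replaced, MK-4280 exposure on the equal split is 96 + 30 = 126, and 30/126 = 23.8%. Sections 5.2 and 10.1 say only that they may be replaced. With none replaced, the 800 mg count would be 96 − 30 = 66, and the share 30/(66 + 30) = 31%. Of all 318 treated, they are 30/318 = 9.4%.

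**Step 6: the two definitions side by side.** ASaT has no dose limit and includes the 30. The Section 10.1 definition covers all of Section 10. It names efficacy, futility, sample size and power as examples without limiting itself to them, and gives way only where more detail is provided. ASaT alone does not decide the matter: Section 10.5.1 uses the same population for efficacy, where Sections 10.1 and 10.7 nevertheless set the 30 apart. Section 10.6.2 is where safety detail would be expected, and it provides none.

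**The case against.** The strongest reply is that nothing forbids a pooled table. The objective first speaks of each combination, the by-group sentence follows, and the analysis is descriptive, so the same data can be laid out either way. This is true, and it limits the point to what is planned. But the only layout the plan commits to is the by-group one.

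A reader might go further and infer that a toxicity has to be found afresh in each cell, because Section 7.3.1 gives an "opportunity to drop individual treatment combinations within biomarker-defined groups or entire biomarker-defined groups for futility or safety". The documents do not support that. Section 7.3.1 and the interim analysis row of Section 10.1 state the level at which a combination may be dropped, not that only that cell's data inform the decision. No numerical safety rule exists: interim analyses use ORR, and the termination list in Section 10.7 covers futility and maximum numbers. Section 9.3.5 has the Sponsor monitoring aggregated safety data, Section 9.3.4 requires serious events to be reported within 24 hours, and the trial is open-label. Ongoing surveillance is not confined to cells; the weakness is in the planned summary.

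A reader might also infer that the plan excludes the 30 starters from safety. That is not established either: ASaT includes everyone treated, and the Section 10.1 definition carries an exception clause and does not name safety. What stands is an unresolved conflict.

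Finally, a pooled table can hide a difference confined to one biomarker group. That is a reason to keep the by-group tables, not to omit the pooled one.

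**Conclusion.** The point holds as a defect in the planned safety summary. The stated assessment rests on 12 cells averaging 22 or 30, while the same data pooled by combination would cut the zero-event upper bound from 12.7% (n = 22) to 3.1% (n = 96), and narrow an interval around an illustrative 20% rate from about 5-40% to about 12-29%. These figures assume an equal split and no arm dropped; pooling also treats toxicity as broadly similar across groups.

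Separately, Section 10 leaves open whether the 30 participants who started at 200 mg are in the MK-4280 safety tables, and how those who switched are shown. They are about 24% of those exposed to MK-4280 if all are replaced, and a larger share if fewer are. This is the size of the ambiguity, not a known loss.

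Neither issue touches the primary endpoint, data collection or ongoing safety monitoring.

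**What to change.** 1. In Sections 1, 4 and 10.6.2, add a safety summary per combination pooled over the four biomarker groups and name it as the main safety table. Keep the by-group tables as secondary.
2. Reconcile Section 10.1 with Sections 10.5.1 and 10.5.2 by stating that the restriction to 800 mg from C1D1 does not apply to safety.
3. In 10.6.2, show participants who started MK-4280 at 200 mg in their own column. For those who switched, present adverse events by the MK-4280 dose at onset.

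The cost is a few sentences and some extra tables from data already collected. The one statistical downside, that pooling may mask a group-specific difference, is covered by the retained by-group tables.
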